5.2 Secondary Objectives

- 1) The overall safety of belzutifan, including safety concerns, in subjects with RCC
- 2) The effectiveness of belzutifan in subjects with RCC

To address the Secondary Objectives, the following points will be addressed:

- a) To describe the patient demographic and baseline clinical characteristics in;
 - In the registered subjects
 - in the safety evaluation group
 - by presence/absence of any AEs
 - by presence/absence of hemorrhage
 - by presence/absence of fracture
 - by presence/absence of anemia
 - by presence/absence of hypoxia.
 - by presence/absence of intracranial lesions
- b) To describe separately the incidence of a) anemia and b) hypoxia, the incidence of AEs including all AEs, ADRs, grade 3-5 AEs, grade 3-5 ADRs, SAEs and SADR
- c) To describe the proportion of subjects of intracranial hemorrhage AEs including all AEs, ADRs, grade 3-5 AEs, grade 3-5 ADRs, SAEs and SADR with or without pre-existing intracranial lesions
- d) To describe the overall incidence and outcomes of AEs, ADRs, grade 3-5 AEs, grade 3-5 ADRs, SAEs, SADR, unexpected SAEs, and unexpected SADR;
- e) For hemorrhage AEs, fracture AEs, anemia AEs, hypoxia AEs, all AEs, All SAEs, All ADRs, all SADR:
 - To describe the proportion of subjects who interrupt drug due and the reasons for drug interruption;
 - To describe the proportion of subjects who discontinue drug and the reasons for drug discontinuation;
 - To describe the proportion of subjects with dose reduction and the reasons for dose reduction;
- f) To describe a) objective response rate (ORR) and b) disease control rate (DCR) in subjects that receive the recommended dose.

6 STUDY METHOD

6.1 Study Design

This is a non-interventional, descriptive, longitudinal, multi-center collaborative study.

The study includes subjects in Japan with radically unresectable or metastatic renal cell carcinoma who have received belzutifan in routine clinical practice as indicated by the current local label. There is no comparator arm.

At each site, subjects that meet the inclusion/exclusion criteria will be approached for informed consent. Subjects may be prospectively identified and registered/enrolled at the time of treatment initiation or retrospectively identified and registered/enrolled after treatment initiation but before the end of the registration period.

Study-specific CRFs will be completed by investigator or healthcare practitioners and the investigator will submit using an electronic data capture (EDC) system. Patient and treatment data will be sourced from the patient's medical records.

In the registration form/CRF, the site will enter a unique number (patient identifier), which only the treating investigator and/or authorized personnel will be able to use to identify the patient. Common to all CRFs for the patient will be a case registration number, which will be used by the Sponsor to manage the cases.

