6.5.5 Safety endpoints and effectiveness endpoints collection

The investigator / program coordinator at each site will monitor for the occurrence of any endpoints specified within this protocol through the on-site visit, scheduled contacts, e-mails, telephone calls, and/or review of the medical records during the treatment and observation periods.

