6.9.2 Primary Objective analysis

The incidence of hemorrhage AEs and the incidence fracture AEs reported by investigator, including all AEs, ADRs, grade 3-5 AEs, grade 3-5 ADRs, SAEs, and SADR will be analyzed and reported as categorical variables.

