6.10 Limitations of the methodology

Due to its observational nature, there are several potential sources of bias including selection bias and information bias. In terms of potential selection bias, the study sites willing to participate in the study may not be fully representative of all sites treating patients of interest in Japan and may be different from patients treated in other healthcare systems in Japan or

other countries. As for information bias, there can be information loss during medical chart abstraction, based on recall, or transcription of information for database capture. As well, the adverse events are based on investigator reports and not defined by specific diagnostic tests. Additionally, causality assessment is decentralized and assessed by each investigator, therefore there may be differences in conclusions by investigator. Furthermore, as it relates to effectiveness data, response assessments may not be based on validated nor standardized measures (e.g., RECIST v.1.1). Lastly, the association of outcomes with treatment cannot be directly evaluated in this study given the lack of an internal comparator and inability to control for confounders or effect modifiers. There is also limited power and precision given the small sample size. As a result of the potential biases and limited power/precision, all analyses are descriptive in nature. Overall, these results offer a limited view of the safety/effectiveness of belzutifan and cannot be statistically compared to previous trials or other observational reports and should be interpreted with caution.

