8 MANAGEMENT OF ADVERSE EVENT AND REPORTABLE INFORMATION

Introduction

This is a hybrid data collection non-interventional study being conducted within routine medical practice. All direction for medication usage is at the discretion of a investigator in accordance with usual medical practice. No administration of any therapeutic or prophylactic agent is required in this protocol.

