Appendix 1. Reporting of Other safety information/ Product Quality Complaint

If PQCs, or special situations are identified following use of belzutifan, then they must be reported per the table below. Additionally, any SAEs and/or NSARs for belzutifan that occur more than 30 days after the end of administration must also be reported per the table below, if identified.

While SAEs, NSARs, special situations and PQCs for *other* Sponsor products are not solicited, they must be reported to the Sponsor according to the table below if identified.

Table 1A AE/PQC Reporting Timeframes and Process for Investigators

Reportable information	Reporting timeframe Investigator to Sponsor	Reporting method
SAE (Primary Data) SADR (Secondary Chart Review) PQC Special situation	24 hours from receipt	If AE(s) occurs during the observation period, the investigator should promptly notify the MR, without waiting for the end of the observation period per the noted reporting timeframe by: 
 • Filling in the(e)CRF and submitting it • Contacting the MR in charge
NSADR	10 CD from receipt	

Study Report:

The final study report will include a summary of all reported AEs and special situations collected for belzutifan, and will be provided to regulatory agencies by the sponsor as required.

Periodic Safety Update Reports:

Any relevant safety information will be summarized and the Sponsor will include in the appropriate Periodic Safety Reports (PSUR/DSUR) if required.

Additional Definitions:

Adverse Reaction (AR); also referred to as Adverse Drug Reaction (ADR)

An AE which has a causal relationship with the product, that is, a causal relationship between the product and the adverse event is at least a reasonable possibility.

Serious Adverse Event (SAE) Serious Adverse Reaction (SAR)

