10.7	Does the plan describe methods for handling missing data?				6.5
10.8	Are relevant sensitivity analyses described?				

Comments:

--

Section 11: Data management and quality control	Yes	No	N/A	Section Number
11.1 Does the protocol provide information on data storage? (e.g. software and IT environment, database maintenance and anti-fraud protection, archiving)				6.8
11.2 Are methods of quality assurance described?				Part B Section 1
11.3 Is there a system in place for independent review of study results?				3 See below (1)

Comments:

(1) A final report will be shared with the Japan PMDA

Section 12: Limitations	Yes	No	N/A	Section Number
12.1 Does the protocol discuss the impact on the study results of:				
12.1.1 Selection bias?				6.10
12.1.2 Information bias?				6.10
12.1.3 Residual/unmeasured confounding? (e.g. anticipated direction and magnitude of such biases, validation sub-study, use of validation and external data, analytical methods).				
12.2 Does the protocol discuss study feasibility? (e.g. study size, anticipated exposure uptake, duration of follow-up in a cohort study, patient recruitment, precision of the estimates)				6.3, 6.4

Comments:

--

Section 13: Ethical/data protection issues	Yes	No	N/A	Section Number
13.1 Have requirements of Ethics Committee/ Institutional Review Board been described?				7
13.2 Has any outcome of an ethical review procedure been addressed?				See below (1)

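### The primary hemorrhage and fracture percentages pool subjects registered at treatment start with subjects registered later, and the protocol names no breakdown by registration timing

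*Protocol*

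**What the plan says.** **Registration.** Section 6.1, repeated in Section 6.5.3, allows registration at treatment initiation or "retrospectively identified and registered/enrolled after treatment initiation but before the end of the registration period". Section 6.2 admits subjects first treated after approval on 24-JUN-2025. Section 3 opens registration in APR 2026 and closes it in MAR 2029.

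**Collection.** Every subject has the same study-specific CRF; Section 6.1 states "Patient and treatment data will be sourced from" the medical records. Section 6.5.5 has the site look for endpoints through "on-site visit, scheduled contacts, e-mails, telephone calls, and/or review of the medical records during the treatment and observation periods". Section 8 describes the whole as follows: "This is a hybrid data collection non-interventional study being conducted within routine medical practice". Grade and causality are assigned by the investigator for every AE (Section 6.7.4).

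**Analysis.** The primary analysis in Section 6.9.2 is "The incidence of hemorrhage AEs and the incidence fracture AEs reported by investigator", in the categories all AEs, ADRs, grade 3-5 and serious, over the safety set. Section 6.9.3 lists eight groupings for the demographic and clinical characteristics; registration timing is not among them. Section 5.1 sets the primary percentages against the everolimus group of Study 005, and Section 6.9.4 makes that comparison qualitative.

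**Limitations.** Section 6.10 says that "there can be information loss during medical chart abstraction, based on recall, or transcription of information for database capture". The checklist in Annex 1 answers No at item 10.6 (analytic control of outcome misclassification) and No at item 10.8, "Are relevant sensitivity analyses described".

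**The concern.** A subject registered at first dose can be asked about bleeding or a fall at each contact, and the event can be graded and judged as it happens. For a subject registered months later, the period before registration is covered only by what was written down for routine care and by what the site remembers. Minor bleeds, and judgments on whether the drug caused them, are the items most likely to be missing.

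Any such shortfall runs in one direction: it lowers the belzutifan percentage. That percentage is then set beside an arm of a phase 3 trial and informs the review of the risk management plan foreseen in Section 3. With a single pooled figure, a reader cannot tell how many subjects were registered late or whether they pull the result down.

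**Working it through.** **1. The plan's own figure.** Section 6.3 asks for at least 11 subjects with Grade 3 or higher hemorrhage with over 90% probability at an incidence of 3.8%. By the exact binomial, P(X ≥ 11 | n = 403, p = 0.038) = 0.9005, and at n = 402 it is 0.8988. So 403 reproduces. It assumes that the survey captures events as completely as Study 005 did.

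**2. Late registration is built in.** Section 3 gives only the month of opening; take 1 April 2026. From 24 June 2025 that is 281 days. All subjects starting in this interval are registered after first dose.

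**3. Many of their events may precede registration.** Section 6.5.4 gives the Study 005 median time to first event as 84 days for hemorrhage and 277.5 days for fracture. A subject who started before 7 January 2026 has more than 84 days behind them when registration opens. If timing follows Study 005, at least half of the first hemorrhages that such subjects have within the 52-week window fall before registration. For the earliest starters (281 days) the same holds for fractures. Even so, no 52-week window has closed when registration opens: a start on 24 June 2025 reaches week 52 on 23 June 2026.

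**4. Effect on the pooled percentage.** Let p be the true percentage, f the share of late-registered subjects and s the fraction of their events that is captured, relative to full capture in the others. Then

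pooled % = p × (1 − f × (1 − s)).

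The p values are the Study 005 rates that Section 6.3 assumes for the survey (hemorrhage 12.6%, fracture 4.8%, Grade 3+ hemorrhage 3.8%). Both f and s are assumptions; the protocol gives neither.

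| f | s | factor | hemorrhage % | hemorrhage cases in 403 | fracture % | P(≥ 11 Grade 3+ hemorrhages) |
|---|---|---|---|---|---|---|
| 0 | – | 1 | 12.6 | 50.8 | 4.8 | 0.90 |
| 0.25 | 0.9 | 0.975 | 12.3 | 49.5 | 4.7 | 0.88 |
| 0.50 | 0.7 | 0.85 | 10.7 | 43.2 | 4.1 | 0.75 |
| 0.75 | 0.6 | 0.70 | 8.8 | 35.5 | 3.4 | 0.51 |

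About 1 to 15 of 51 expected hemorrhage cases would go uncounted. The last column applies the same s to Grade 3+ events, which is pessimistic because severe events are more likely to be in the record. With f = 0.10 and s = 0.9 the effect is negligible (12.6% reads 12.5%).

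**5. What a split can show.** With 202 subjects per group at Study 005 rates, the exact 95% intervals are 8.6% to 18.3% for hemorrhage (26/202) and 2.4% to 8.9% for fracture (10/202). With all 403 subjects, hemorrhage (51/403) has 9.6% to 16.3%.

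**The case against.** A reader might infer that the two groups are measured with two different instruments, especially from Appendix 1, Table 1A, which separates "SAE (Primary Data) SADR (Secondary Chart Review"). The protocol does not support that. One CRF, one record source and one rule for grading and causality serve all subjects. Table 1A covers information outside the survey, such as quality complaints, special situations and events more than 30 days after treatment ends. Survey AEs are governed by Table 6 in Section 8.1, which makes no such distinction.

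A reader might also infer that late-registered subjects are wholly reconstructed from charts, or that under-recording is an established fact. Neither follows. A late-registered subject is followed forward for whatever remains of the 52 weeks, and a subject registered on day 15 has nearly all follow-up ahead. A fixed cut of, say, 14 days would therefore mislabel many subjects. The model in step 4 shares this weakness, since it applies s to all events of a late-registered subject and so overstates the loss for those registered soon after first dose.

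Three further points deserve weight. The analysis plan, not shown, may contain the split, and the checklist answers describe the protocol only. Section 6.9.4 already rules out formal testing and requires limits on comparability to be reported. And the intervals are wide: 8.6% to 18.3% includes the 8.8% that 70% capture would give (12.6% × 0.7), so the table could miss a real shortfall.

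These points limit the claim without removing it. Section 6.10 names abstraction loss without tying it to registration timing, and a limitation stated in words does not tell the reader how many subjects or events it touches.

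**Conclusion.** The point holds as a modest one. The protocol allows two registration timings, makes late registration unavoidable for about the first nine months after approval, and names no breakdown of the primary percentages by that timing. Any poorer capture before registration would bias the pooled figure downward, toward a reassuring contrast with Study 005.

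The size is unknown. The range of 12.3% to 8.8% for a true 12.6% rests entirely on assumed shares (25% to 75%) and capture rates (90% to 60%), and on full capture in subjects registered at initiation. With a small late-registered share it would hardly matter. The protocol also does not give the everolimus percentage, so whether such a shift would change the contrast cannot be judged. This is an improvement worth making, not an error that invalidates the primary result.

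**What to change.** In Section 6.9.2, keep the overall percentage as the primary result and add:

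- the number of subjects registered at initiation and the number registered later, with the distribution of the interval from first dose to registration;
- each primary endpoint (all AEs, ADRs, grade 3-5 and serious, for hemorrhage and for fracture) tabulated by that interval;
- for late-registered subjects, events counted separately by onset before or after registration, so that subjects mostly followed forward are not treated as chart reconstructions.

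In Section 6.9.4, show the registered-at-initiation subset descriptively beside the Study 005 contrast. In Section 6.10, tie the abstraction and recall limitation to the period before registration.

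The cost is small. The first-dose date is entered on the EDC registration form (Section 6.5.3), AE onset date is a CRF item (Section 6.6), and the registration date should be available as the submission date of that form. No new data collection or testing is needed. The price is wide intervals within each group and very few Grade 3+ fractures in either, since Section 6.3 anticipates only 5 in total. The text should say that the table is a descriptive check and that similar percentages in the two groups do not prove equal capture.

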6.2 Study Subjects

1) Inclusion criteria

- Subject who is indicated according to the local label of belzutifan and decision to receive the product is made independent of this protocol
- Subjects who are Japanese subjects with RCC, excluding those with Von Hippel-Lindau disease-associated RCC
- Subject who is administered with belzutifan for the first time following its approval on 24-JUN-2025 for RCC as part of routine clinical practice

2) Exclusion criteria

- Subject who has a known contraindication according to the local label of belzutifan
- Subjects previously treated with belzutifan before 24-JUN-2025 are excluded from this survey, as are any subjects that receive belzutifan as part of a clinical trial
- Subjects with Von Hippel-Lindau disease (VHL)-associated RCC

6.3 Planned Subject Number

A sample size of 403 subjects (safety analysis set) is planned to address the objectives of this Study.

This number of subjects was agreed upon with PMDA. This sample size was determined a priori and was not calculated as part of the development of this protocol.

Rationale

In the global Phase 3 clinical study in subjects with advanced RCC MK-6482-005/LITESPARK-005 (Study 005), The incidence of hemorrhage-related adverse events was 12.6% (47/372 subjects), with Grade 3 or higher being 3.8% (14/372 subjects). The incidence of fracture-related adverse events was 4.8% (18/372 subjects), with Grade 3 or higher being 2.2% (8/372 subjects).

To detect 11 or more subjects of Grade 3 or higher hemorrhage-related adverse events, which occurred at an incidence rate of 3.8% in Study 005, with a probability of over 90%, a sample size of 403 subjects is required. Assuming that the incidence of adverse events for the safety evaluation items after marketing is equivalent to that in the 005 trial and setting the number of subjects for safety analysis at 403 it is possible to collect 42 subjects with hemorrhage of which 11 subjects would be anticipated to be Grade 3 or higher; 14 subjects with fractures of which 5 subjects would be anticipated to be Grade 3 or higher; 325 subjects with anemia of which 119 subjects would be anticipated to be Grade 3 or higher; 49 subjects with hypoxia of which 35 subjects would be anticipated to be Grade 3 or higher, with 90% probability under actual usage conditions. Considering dropouts and loss to follow-up, it is thought that registering 410 subjects will ensure 403 subjects for safety analysis. By setting the number of subjects for safety analysis at 403 subjects, it is anticipated to detect the occurrence of hemorrhage, fractures, anemia, and hypoxia under routine clinical practice.

6.4 Planned Site

Site(s) will be evaluated and selected based on availability of sufficient target subject pool, appropriate resources such as facilities and staffs and/or experienced investigator to address the objectives of this Study. Details on the total number of planned sites and general types of institutions is as follows:

Number of planned site(s)	Approximately 150 sites
Target institute / department at site(s)	Urology and oncology departments at general hospitals/clinics in Japan that treat subjects with RCC

6.5 Study Method

Procedures and activities during this study are outlined in [Table 1](#).

Table 1 Schedule of Activities

Timing of implementation Item	Before the start of administration	Observation Period (Up to a Maximum of 12 Months)				Note
		During administration	At the end of administration	From the end of administration until 30 days after the end of administration	End of observation phase (12 months)	
Informed consent / Privacy statement	X					
Inclusion/Exclusion criteria review	X					
Subject characteristics and indication(s) for use	X					
Medical history and Concurrent condition	X					For liver dysfunction, The Child-Pugh classification (Table 2) is used. Points are assigned to each item, and the total score is classified based on Table 3 .
Condition of RCC before belzutifan Administration	X					
Prior Treatment for RCC before belzutifan Administration	X					

Timing of implementation Item	Before the start of administration	Observation Period (Up to a Maximum of 12 Months)				Note
		During administration	At the end of administration	From the end of administration until 30 days after the end of administration	End of observation phase (12 months)	
Treatment with belzutifan		X	X			
Concomitant medications/Concomitant therapies		X	X	X		Concomitant medications/therapies for RCC used during belzutifan administration period, and AE/ prophylactic use during the administration period or within 30 days after discontinuation of belzutifan.

Timing of implementation Item	Before the start of administration	Observation Period (Up to a Maximum of 12 Months)				Note
		During administration	At the end of administration	From the end of administration until 30 days after the end of administration	End of observation phase (12 months)	
Effectiveness		X	X	X	X	Effectiveness assessments will be conducted until disease progression, initiation of other anti-cancer therapies, death, or loss to follow-up, whichever occurs first. However , the maximum assessment period will not exceeding the observation period [12 months (52 weeks) from the first belzutifan treatment date].
Status on the date of last observation					X	At 12 months (52 weeks) from the start of belzutifan administration; however, in cases where death or lost to follow-up occurs within 12 months from the start of belzutifan administration, the date of confirmation of these events shall be considered.
Adverse Event		X	X	X		Refer to Table 4 , Table 5 and Table 6 for supplementary notes related to AEs.

Timing of implementation Item	Before the start of administration	Observation Period (Up to a Maximum of 12 Months)				Note
		During administration	At the end of administration	From the end of administration until 30 days after the end of administration	End of observation phase (12 months)	
Laboratory data/test	X	X	X	X		Laboratory test values and examinations related to AEs will be collected in this survey.

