
Study subjects
	
Subjects in Japan with RCC (not Von Hippel-Lindau disease (VHL)-associated) who have received belzutifan in routine clinical practice for the first time as indicated by the current local label.

Planned subject number
	
403 subjects (safety analysis set)

Study method
	
The study will be conducted with the use of EDC system by means of a central registration method. At each site, subjects that meet the inclusion/exclusion criteria will be approached for informed consent. Subjects may be prospectively identified and registered/enrolled at the time of treatment initiation or retrospectively identified and registered/enrolled after treatment initiation but before the end of the registration period.

Endpoint and its measurement
	
Safety endpoints will include investigator reported adverse events, summarized by frequency and severity, and for secondary effectiveness endpoints, response to treatment by local investigator assessment.

Data Analysis
	
Study endpoints will be analyzed using descriptive statistical methods such as mean, standard deviation, median, interquartile range, and/or minimum/maximum/range for continuous variables. For any categorical variables, e.g., AE analysis, frequency and percentage will be reported. There is no hypothesis testing.
 
To assess whether demographic and/or clinical characteristics impact safety endpoints, these characteristics will be analyzed using descriptive statistical methods and reported for all registered subjects, the safety evaluation group, and presence/absence of AEs/select protocol-specified AEs.
 
Details of the statistical analysis will be specified separately in the statistical analysis plan.

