6.6 Study Item

As possible, all the data for the following items will be collected in this study.

Category	Collection item
Subject characteristics and indication(s) for use	
 • Anonymized ID Number • Sex • Month/year of birth (or Age at the start of belzutifan administration) • Indication for use • Start date of treatment with belzutifan • Inpatient/outpatient (at the start of belzutifan administration) • Height • Weight • Smoking status • Pregnancy status at the start of administration of belzutifan (female only) • Lactation status at the start of administration of belzutifan (female only) • Karnofsky Performance Score (KPS) at the start of administration of belzutifan • Eastern Cooperative Oncology Group (ECOG) Performance status at the start of administration of belzutifan

Category	Collection item
Medical history and co-morbid condition	
 • For select conditions (e.g., liver dysfunction, renal dysfunction, respiratory diseases, cardiac diseases, osteoporosis, and others), whether they were previously present and cured versus an ongoing co-morbidity will be recorded, as well as some details on the disease/severity. 
For hepatic impairment, Grade information will also be collected using the Child-Pugh² classification. Please refer to Table 2 and Table 3 for details on the grading.

Condition of RCC before belzutifan Administration	
 • Date of diagnosis (at initial diagnosis, at most recent recurrence diagnosis) • TNM Staging System (at initial diagnosis, at most recent recurrence diagnosis) • International Metastatic Database Consortium (IMDC) Risk Classification • Histological subtype (i.e., ccRCC vs nccRCC) • Site of recurrence or metastasis at most recent diagnosis • Treatment line at the time of starting administration of belzutifan (including belzutifan)
Prior Treatment for RCC before belzutifan Administration	
 • Prior medications • Prior radiotherapy • Prior surgeries • Other prior treatments
Treatment of belzutifan	
 • Initiation date of belzutifan • The date of any dose for belzutifan and stop date of belzutifan after Day 1 • Daily dose • Action taken with belzutifan (e.g., dose interruption/daily dose change) • Reason for dose interruption/reason for daily dose change (if applicable)

² [1]

Category	Collection item

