Test	
 Name of test (including imaging) Date of test performed Test result/findings

Table 2 Child-Pugh classification

Score	1 point	2 points	3 points
Hepatic Encephalopathy	None	Mild (Grade I · II)	Coma (Grade III≤)
Ascites	Absent	Slight	Moderate
Serum Bilirubin (mg/dL) ⁶	<2.0	2.0-3.0	3.0<
Serum Albumin (g/dL)	3.5<	2.8-3.5	<2.8
Prothrombin Time Activity (%)	70<	40-70	<40
INR	<1.7	1.7-2.3	2.3<

Table 3 Child-Pugh Total Score

Class	Total Score
Class A	5-6 points
Class B	7-9 points
Class C	10-15 points

[1]

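### Table 2 gives six scored Child-Pugh rows while Table 3 classifies a five-item total, so a site following the instruction literally counts coagulation twice

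*Protocol*

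**What the plan says.** Three places in the Protocol have to work together.

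- **Table 1 (section 6.5), row on medical history and concurrent conditions.** For liver dysfunction the Child-Pugh table is to be used: "Points are assigned to each item, and the total score is classified based on" Table 3.
- **"Table 2 Child-Pugh classification" (section 6.6).** As read, it lists six rows, each with its own cut-offs for 1, 2 and 3 points: encephalopathy, ascites, bilirubin, albumin, "Prothrombin Time Activity" and INR. Its only footnote concerns bilirubin in cholestasis.
- **Table 3 (section 6.6).** Class A is 5-6 points, Class B is 7-9 and Class C is 10-15.

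The use of the score is stated in the section 6.6 row on medical history and co-morbid conditions. For hepatic impairment, "Grade information will also be collected using the Child-Pugh" classification. Section 6.9 includes medical history and comorbidities in the patient background summary. Section 6.9.3 tabulates clinical characteristics overall and by presence or absence of several events, without naming the Child-Pugh class.

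**The concern.** The instruction, the item table and the class table cannot all be followed at once. If every row of Table 2 is scored, the sum is on a different scale from the one Table 3 classifies, and it is always higher than the five-item sum. If only one coagulation row is scored, Table 3 fits, but the reader has to infer that rule.

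What is at stake is whether the hepatic grade means the same thing at every site. About 150 sites are planned (section 6.4), and each would settle the ambiguity for itself. The section 6.6 list of haemorrhage-related tests names PT, PT/INR and APTT, so a subject with both coagulation results is foreseeable.

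The grade may also be hard to correct afterwards. The listed items collect the grade, while section 6.6 and Table 1 restrict laboratory data to results related to adverse events. The sponsor may therefore lack the component values needed to re-derive a class. The CRF is not shown, so this is a possibility and not a finding.

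**Working it through.** **Inputs.** Each Table 2 row scores 1, 2 or 3 (section 6.6). Class limits are 5-6, 7-9 and 10-15 (Table 3). The rule is to score every item and sum (Table 1). No error rate or power figure is involved; the synopsis states "There is no hypothesis testing".

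**Step 1: reproduce the Table 3 range.** With k items the total runs from k × 1 to k × 3.

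- Five items (one coagulation score): 5 to 15. This matches Table 3 exactly.
- Six items (Table 2 as read): 6 to 18. This does not match. A total of 5 is unreachable, and 16, 17 and 18 have no class.

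**Step 2: effect on a given subject.** Take the five-item total and add the points of the second coagulation row, which are at least 1 and at most 3.

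- Five-item total 6 (Class A): 6 + 1 to 6 + 3 = 7 to 9, always Class B.
- Five-item total 9 (Class B): 9 + 1 to 9 + 3 = 10 to 12, always Class C.

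These two results hold whether or not the two tests earn the same points, and even when coagulation is normal. Because at least one point is added, no subject can move to a better class.

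**Step 3: all score patterns, assuming PT activity and INR earn equal points.** There are 3^5 = 243 five-item patterns: 6 in Class A, 90 in B and 147 in C. The four non-coagulation items sum to 4, 5, 6, 7, 8, 9, 10, 11 and 12 in 1, 4, 10, 16, 19, 16, 10, 4 and 1 ways.

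| Five-item total | Coagulation points | New total | Change | Patterns |
|---|---|---|---|---|
| 5 | 1 | 6 | stays A | 1 |
| 6 | 1 or 2 | 7-8 | A to B | 4 + 1 = 5 |
| 7 | 1 or 2 | 8-9 | stays B | 10 + 4 = 14 |
| 7 | 3 | 10 | B to C | 1 |
| 8 | 1 | 9 | stays B | 16 |
| 8 | 2 or 3 | 10-11 | B to C | 10 + 4 = 14 |
| 9 | 1, 2 or 3 | 10-12 | B to C | 19 + 16 + 10 = 45 |
| 13 | 3 | 16 | C to no class | 10 |
| 14 | 2 or 3 | 16-17 | C to no class | 1 + 4 = 5 |
| 15 | 3 | 18 | C to no class | 1 |

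All other Class C patterns stay in C.

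- A to B: 5 of 6.
- B to C: 1 + 14 + 45 = 60 of 90.
- C to no class: 10 + 5 + 1 = 16 of 147.
- Changed in all: 5 + 60 + 16 = 81 of 243. Unchanged: 243 − 81 = 162.

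These are counts of possible score combinations. They show where the class limits are sensitive and say nothing about how many subjects are affected.

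**The case against.** **Layout.** The table was read from PDF by a program. A merged coagulation cell in the printed table would come out as exactly these two adjacent lines, and this cannot be excluded. Even so, the text contains no wording that only one of the two is scored.

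**The range gives the answer away.** Table 3 starts at 5, which six items cannot reach, and the Protocol cites a published source for the score. A careful investigator will infer five items. This stands in part: many sites may score correctly. It also means that some may score one test and others both, which is the inconsistency at issue.

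**Checks downstream.** Section 6.5.8 has the sponsor verify forms and query sites. A total of 16 to 18 should be noticed. A total that is 1 to 3 points too high but still within 5-15 might not be. The EDC may already total five items; the documents do not show it.

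**Stronger readings that do not hold.** A reader might take 81 of 243 to mean that a third of subjects are misgraded. That would require every pattern to be equally likely, both tests to be available, scored and always worth equal points, and every subject to have liver dysfunction. The documents support none of this, and a subject normal on every item goes from 5 to 6 and stays in Class A. A reader might also infer that the error is differential with respect to bleeding, since coagulation is the doubled component. The class is recorded before administration, and nothing links having both tests to later haemorrhage, fracture, anaemia or hypoxia.

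**Conclusion.** The inconsistency is real on the text as read: the literal rule yields 6 to 18, and the class table covers 5 to 15. Where a site has both results and scores both, a five-item total of 6 always becomes Class B and a 9 always becomes Class C, 16 to 18 cannot be classified, and grading differs from that at sites scoring one test.

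The severity is minor. The class does not enter the study-specific eligibility criteria (section 6.2), the sample size (6.3), the endpoints (6.7.1 and 6.7.2) or the analysis sets (6.9.1). It affects only the descriptive baseline account of hepatic impairment, in a subset of unstated size. Its tabulation by event is inferred from the general wording of section 6.9.3. No share of subjects affected and no outcome-related bias can be claimed. The conclusion assumes that the two coagulation rows are printed separately, as they appear in the text, and that no guidance outside the Protocol says to score only one.

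**What to change.** Reconcile Tables 1, 2 and 3 with one line under Table 2: PT activity and INR form a single coagulation item of which only one is scored, with the precedence chosen by the sponsor when both are available. The instruction in Table 1 then agrees with Table 3, and every possible total has a class. Add an EDC check that the total comes from five items and lies between 5 and 15, or confirm that one exists.

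The cost is one line of text and one edit check, with no added data collection. It is best done before registration opens (planned for April 2026, section 3), because the grade may not be re-derivable later from the laboratory data listed for collection.
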